7. STUDY PLAN

7.1 Study Schedule

	ICU stay period					ICU discharge	Last FUP
Poractant alfa treated group	Screening ⁷	Day 1 (Randomisation)	Day 2	Day 3	Day 4 – 27	Day X	Day 28
		Before randomisation/treatment and 6-12-24h after each administration up to 72 hours			Every 24h till ICU discharge	Whenever it occurs	
Control group	Screening	Time 72 h			Day 4 – 27	Day X	Day 28
		Before randomisation and at 6, 12, 24, 30, 36, 48, 54, 60, 72 h since randomisation			Every 24h till ICU discharge	Whenever it occurs	
Assessments							
Informed consent	X						
Inclusion and exclusion criteria	X						
Demography	X						

Clinical Study Code No.: CLI-050000-04	Version No.: 4.0
EUDRACT No.: 2020-002632-75 – IND No: 153286	Date: 02 MAR 2021

Poractant alfa treated group	ICU stay period					ICU discharge	Last FUP
	Screening ⁷	Day 1 (Randomisation)	Day 2	Day 3	Day 4 – 27	Day X	Day 28
		Before randomisation/treatment and 6-12-24h after each administration up to 72 hours			Every 24h till ICU discharge	Whenever it occurs	
Control group	Screening	Time 72 h			Day 4 – 27	Day X	Day 28
		Before randomisation and at 6, 12, 24, 30, 36, 48, 54, 60, 72 h since randomisation			Every 24h till ICU discharge	Whenever it occurs	
Vital signs (blood pressure, heart rate)	X	Once Treated group: 24 - 48 - 72h post start of treatment Control group: 24 - 48 - 72h post randomisation			X	X	X
Full physical examination including height and weight	X						
Medical history (SARS COVID-19 ADRS, past and current relevant medical conditions)	X						
Arterial Blood Gas (ABG) Analysis ¹	X (If the screening assessment is done just before randomization no need to repeat the assessment)	Treated group: Before randomisation and 6-12-24h after each administration up to 72 hours Control group: Before randomisation and at 6, 12, 24, 30, 36, 48, 54, 60, 72h since randomisation			Every 24h	X	Once if not discharged from ICU
Respiratory support assessment Ventilator parameters ²	X (If the screening assessment is done just before randomization no need to repeat the assessment)	Treated group: Before randomisation and 6-12-24h after each administration up to 72 hours Control group: Before randomisation and at 6, 12, 24, 30, 36, 48, 54, 60, 72h since randomisation			Every 24h	X	Once if not discharged from ICU

Clinical Study Code No.: CLI-050000-04	Version No.: 4.0
EUDRACT No.: 2020-002632-75 – IND No: 153286	Date: 02 MAR 2021

Poractant alfa treated group	ICU stay period					ICU discharge	Last FUP
	Screening ⁷	Day 1 (Randomisation)	Day 2	Day 3	Day 4 – 27	Day X	Day 28
		Before randomisation/treatment and 6-12-24h after each administration up to 72 hours			Every 24h till ICU discharge	Whenever it occurs	
Control group	Screening	Time 72 h			Day 4 – 27	Day X	Day 28
		Before randomisation and at 6, 12, 24, 30, 36, 48, 54, 60, 72 h since randomisation			Every 24h till ICU discharge	Whenever it occurs	
Mechanics Laboratory assessments ³		Treated group: Before randomisation and 12, 24, 48, 72, after first administration Control group: Before randomisation and 12, 24, 48, 72, after randomisation			Treated group: 96h after first administration Control group: 96h after randomisation		
Laboratory assessments ⁴	X			Once Treated group: 24h post last treatment Control group: 72h post randomisation		X	Once if not discharged from ICU
SOFA score ⁵	X			Once Treated group: 24h post last treatment Control group: 72h post randomisation		X	Once if not discharged from ICU
Thoracic CT scan or Chest XR ⁶	X						
Curosurf administration (intreated group)		Three ET administrations with a 24 hours interval (Day 1, Day 2 and Day 3)					
Concomitant Medications	X	X	X	X	X	X	X

Clinical Study Code No.: CLI-050000-04	Version No.: 4.0
EUDRACT No.: 2020-002632-75 – IND No: 153286	Date: 02 MAR 2021

Poractant alfa treated group	ICU stay period					ICU discharge	Last FUP
	Screening ⁷	Day 1 (Randomisation)	Day 2	Day 3	Day 4 – 27	Day X	Day 28
		Before randomisation/treatment and 6-12-24h after each administration up to 72 hours			Every 24h till ICU discharge	Whenever it occurs	
Control group	Screening	Time 72 h			Day 4 – 27	Day X	Day 28
		Before randomisation and at 6, 12, 24, 30, 36, 48, 54, 60, 72 h since randomisation			Every 24h till ICU discharge	Whenever it occurs	
Adverse Events	X	X	X	X	X	X	X
Ventilatory support	X	X	X	X	X	X	X
Concomitant procedures	X	X	X	X	X	X	X

- ¹ Arterial blood gas (ABG) analysis: pH, pCO₂, pO₂, HCO₃, lactate.
- ² Ventilatory parameters: PaO₂/FiO₂, FiO₂, TV (tidal volume), RR (respiratory rate), Cstat (static compliance), Cdyn (dynamic compliance), PEEP (positive end-expiratory pressure), PIP (peak inspiratory pressure), Pplat (plateau Pressure).
- ³ For mechanics assessments: blood sampling and tracheal aspirates (TA). Bronchoscopic washings performed as clinically indicated only, with surplus samples retrieved for mechanistic study as available. They are planned only for patients recruited in UK.
- ⁴ Blood count, bilirubin, creatinine, eGFR, glucose, AST, ALT, LDH, D-dimer, CRP (C-reactive protein), procalcitonin. Urine beta HCG at screening only.
- ⁵ SOFA score is calculated considering PaO₂/FiO₂, Glasgow coma scale, mean arterial pressure, and bilirubin, platelet and creatinine levels. SOFA score can be calculated only after the patient is included in the study (after the ICF signature) and in case not all the SOFA parameters are available before randomization, the calculation can be based on historical data collected (within 24 hours) as per standard practice.
- ⁶ Already available as part of the standard care procedures.
- ⁷ All screening procedures have to be completed/performed before the randomization.

The following time deviations from theoretical post-dose times will be allowed:

Post-dose time assessments	Allowed deviations
≤ 72 hours	± 1 hour
>72 hours	± 2 hours

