
Study plan
	
After verification of any inclusion/exclusion criteria the patients will be included in the study and randomised to the poractant alfa group or to standard of care one.
 
Poractant alfa group
 
 - Starting from patient intubation and mechanical ventilation, defined assessments will be collected (for details see study schedule 7.1). - Patients will receive three poractant alfa endotracheal administrations 24 hours apart. - Defined assessments will be collected before randomisation and at 6 -12 - 24 hours after each poractant alfa administration till 72 hours since the first administration. - From Day 4 to Day 27 assessment collection will occur every 24 hours until Intensive Care Unit (ICU) discharge. Whenever the discharge occurs, additional safety lab and SOFA assessments will be collected. - At Day 28 the last follow up evaluation will occur on the ICU if still requiring critical care, or by phone call if the patient has been discharged from ICU by that time. 
Control group
 
 - Starting from patient intubation and mechanical ventilation defined assessments will be collected (for details see study schedule 7.1). - Defined assessments will be collected before randomisation and at specific timepoints (according to study schedule 7.1) from

Clinical Study Code No.: CLI-050000-04	Version No.: 4.0
EUDRACT No.: 2020-002632-75 – IND No: 153286	Date: 02 MAR 2021

	
randomisation up to 72 hours.
 
 - From Day 4 to Day 27 assessment data collection (according to study schedule 7.1) will occur every 24 hours until Intensive Care Unit (ICU) discharge. Whenever discharge occurs, assessment data will be collected at the corresponding Day X. - At Day 28 the last follow up evaluation will occur on the ICU, or by phone call if the patient has already been discharged.

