3.2 End of trial definition

A participant is considered to have completed the study if he/she has completed the last scheduled procedure shown in the schedule of assessments: follow up at Day 28. The end of the study is defined as the date of the last follow up visit at Day 28 for the last participant in the trial globally.

Some recruited and treated patients are likely to be transferred during the study period from the ICU to another hospital department for continuation of their clinical care. In this case the patient will remain in the study and relevant data will still be recorded through review of the medical chart or by phone call by the Investigator to the physician of the other department. Similarly checks for the occurrence of any adverse event as well as of any change in relevant concomitant medications will be made and recorded.

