7.1.4 ICU discharge (Day X – whenever it occurs)

- Arterial Blood Gas (ABG) Analysis
- Ventilatory support: extubation date recorded (as applicable) and following ventilation procedures recorded
- Ventilatory parameters: PaO₂/FiO₂, FiO₂, tidal volume (TV), respiratory rate (RR), static compliance (Cstat), dynamic compliance (Cdyn), PEEP (positive end-expiratory pressure), PIP (peak inspiratory pressure), Plateau Pressure (Pplat)
- Laboratory assessments blood count, bilirubin, creatinine, eGFR, LDH, D-dimer, CRP, procalcitonin
- Vital signs will be obtained as appropriate
- SOFA score is calculated considering PaO₂/FiO₂, Glasgow coma scale, mean arterial pressure, and bilirubin, platelet and creatinine levels
- AEs review (including SAEs)
- Concomitant medications and procedure review as applicable
- Discharge date from ICU

7.1.5 Day 28

It's the last day of follow up. Whenever the patient has been discharged home from ICU a phone call FUP is requested.

The following procedures will be followed if the patient is still hospitalized:

- Arterial Blood Gas (ABG) Analysis

Clinical Study Code No.: CLI-050000-04	Version No.: 4.0
EUDRACT No.: 2020-002632-75 – IND No: 153286	Date: 02 MAR 2021

- Ventilatory support: extubation date recorded (as applicable) and following ventilation procedures recorded
- Ventilatory parameters: PaO₂/FiO₂, FiO₂, tidal volume, respiratory rate, static compliance (C_{stat}), dynamic compliance (C_{dyn}), PEEP (positive end-expiratory pressure), PIP (peak inspiratory pressure), Plateau Pressure
- Laboratory assessments: blood count, bilirubin, creatinine, eGFR, LDH, D-dimer, CRP, procalcitonin
- Vital signs will be obtained as appropriate
- SOFA score is calculated considering PaO₂/FiO₂, Glasgow coma scale, mean arterial pressure, and bilirubin, platelet and creatinine levels
- AEs review (including SAEs)
- Concomitant medications review as applicable

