10.8 Recording Adverse Events

All Adverse Events occurring during the course of the study must be documented in the Adverse Event page of the electronic Case Report Form (eCRF). Moreover, if the Adverse Event is serious, the Serious Adverse Event Form must also be completed.

It is responsibility of the Investigator to collect all adverse events (both serious and non-serious) derived by spontaneous, unsolicited reports of patients, by observation and by routine open questionings.

For the purpose of this trial, “acute renal failure” occurrences will not be considered and recorded as adverse events, since well described as a part of the COVID19 syndrome, and highly prevalent in the involved population. They will be recorded as adverse events only if assessed as cause of patient’s death.

The recording period for Adverse Events is the period starting from the date of screening until the patient’s study participation ends.

Clinically significant abnormalities detected at study entry not due to a pre-existing condition or clinically significant changes at the following visits in the medical opinion of the investigator must be reported as adverse events in the eCRF.

If a clinically significant abnormal laboratory finding or other abnormal assessment meets the definition of an AE, then the AE eCRF page must be completed, as appropriate. A diagnosis, if known, or clinical signs and symptoms if diagnosis is unknown, rather than the clinically significant abnormal laboratory finding, should be reported on AE eCRF page. If no diagnosis is known and clinical signs and symptoms are not present, then the abnormal finding should be recorded.

For pharmacovigilance purposes, all SAEs should be followed-up in order to elucidate as completely and practically as possible their nature and/or causality until resolution of all queries, clinical recovery is complete, laboratory results have returned to normal, stable condition is reached or until the patient is lost to follow-up. Follow-up may therefore continue after the patient has left the study. In this case, the follow-up will continue with no timelines for related SAEs, while for unrelated SAEs the type and extent of follow-up undertaken will be determined for each individual case and will depend upon the nature (e.g. events with poor prognosis or which do not resolve), severity and medical significance of the event.

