10.2 Adverse Events

An adverse event (AE) will be classified as follow:

- For poractant alfa group:
 - Pre-treatment AE: if it starts before the first study medication administration (AE onset date/time < date/time of first study medication administration);
 - Treatment emergent AE (TEAE): if it starts on or after the first dose of study medication administration (AE onset date/time \geq date/time of first study medication administration).
- For control group:
 - Pre-treatment AE: if it starts before the randomisation date (AE onset date/time < start date/time of randomisation);
 - Treatment emergent AE (TEAE): if it starts on or after the randomization date (AE onset date/time \geq start date/time of randomisation).

An adverse drug reaction (ADR) is an AE related to study medication. A serious ADR is a serious AE (SAE) related to study medication.

A severe AE is an AE with severe intensity. Refer to Section 7.3 for missing severity.

An AE leading to discontinuation is an AE with action taken with study drug equal to “Drug Permanently Withdrawn”.

An AE leading to death is an AE with outcome equal to “Fatal”.

Pre-treatment AEs, and TEAEs will be presented separately. Pre-treatment AEs will be presented in the listings only.

Two AEs with the same PT and classified in the same category (pre-treatment AE or TEAE) will be considered as two different events when calculating the “number of events” in the tables.

A summary table displaying the number and the percentage of subjects experiencing at least one TEAE, serious TEAEs, non-serious TEAEs, ADRs/drug-related TEAE, serious ADRs, severe TEAEs, TEAEs leading to study drug discontinuation and TEAEs leading to death, as well as the number of events, will be presented by treatment group.

The SOC and PT will also be used for tabulation using the MedDRA dictionary. The number and percentage of subjects with at least one AE and the number of events will be presented by SOC and PT by treatment group for treatment emergent AEs, non-serious TEAEs, serious TEAEs, ADRs, serious ADRs, severe TEAEs, TEAEs leading to treatment discontinuation and TEAEs leading to death.

A table presenting the number and percentage of subjects with at least one TEAE will be provided by PT. The number of subjects with TEAEs will be also displayed by SOC and PT and maximum severity. The number of events will be also included in these analyses.

Tables will be presented by SOC and then by PT, alphabetically sorted.

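### Adverse-event surveillance thins out at ICU discharge, yet the SAP compares crude TEAE counts over the whole follow-up; add TEAE tables for the first 96 hours, when both arms are on near-identical schedules

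*Protocol*

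**What the plan says.** **In ICU.** The Protocol 7.1 schedule heads the Day 4–27 column "Every 24h till ICU discharge". The Study plan in the Protocol Outline has the same rule for the poractant alfa group, "From Day 4 to Day 27 assessment collection will occur every 24 hours until Intensive Care Unit (ICU) discharge", and a parallel one for controls. Blood gases and ventilator parameters are explicitly 24-hourly. Vital signs and adverse events are marked in the same column.

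**How readings become events.** Protocol 10.8 states that "clinically significant changes at the following visits in the medical opinion of the investigator must be reported as adverse events".

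**After ICU.** AE recording does not stop. The schedule row reads "Adverse Events X X X X X X X", and Protocol 10.8 gives the period as "The recording period for Adverse Events is the period starting from the date of screening until the" end of the patient's participation. For patients moved to another department, Protocol 3.2 says "relevant data will still be recorded through review of the medical chart or by phone call by the Investigator", and it also requires AE checks. No frequency is given. For patients at home, Protocol 7.1.5 says "Whenever the patient has been discharged home from ICU a phone call FUP is requested".

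**Safety laboratory tests.** Under the schedule and Section 7.2.1.1 these fall at screening, once at about 72 hours, and then at ICU discharge or Day 28, whichever is earlier. None is scheduled for a patient who has left ICU. Section 7.1.5 can be read as adding one Day 28 panel for patients still in hospital, which does not match the schedule's restriction to patients still in ICU.

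**Analysis.** SAP 10.2 opens the TEAE window at first dose (poractant alfa) or randomisation (control) and states no closing date. Numbers and percentages of subjects, "as well as the number of events, will be presented by treatment group". Tables 14.3.2.1 to 14.3.2.10 have no early window, person-time or split by setting.

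**The concern.** A patient in ICU has frequent scheduled readings, and clinically significant changes in them must be reported as events. A patient on the ward or at home has neither the readings nor a stated interval between checks. Leaving ICU happens after randomisation, and length of ICU stay is itself an efficacy endpoint. Death also ends observation. Both the intensity and the duration of surveillance can therefore differ between arms because of treatment.

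The final SAP is descriptive throughout (SAP 7.5 and 12), so the by-arm AE tables are the main safety comparison. From those tables alone a reader cannot tell fewer events from less observation, or more events from longer survival.

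**Working it through.** The plan states no figure for AE capture. The only related design figures are the 7 versus 11 mean ventilator-free days in Protocol 12.1. Their stated 84% power reproduces (42 versus 28 patients, SD 5.5, two-sided 0.05: 83.6% by noncentral t), and nothing below changes it.

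**Model.** Assume the same true daily event rate in both arms, in and out of ICU. Let *d* be the chance of recording an event after ICU, relative to in ICU. Recorded events are then proportional to ICU days + *d* × days alive after ICU. The documents give neither *d* nor ICU stay by arm, so everything here is illustration.

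**Case A: everyone followed for 28 days, 12 ICU days (poractant alfa) versus 16 (control).** The stays are assumed: 21 − 11 + 2 and 21 − 7 + 2. The ratio, poractant alfa to control, is (12 + 16*d*)/(16 + 12*d*):

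| *d* | Treated | Control | Ratio |
|---|---|---|---|
| 1 | 28 | 28 | 1.00 |
| 0.5 | 20 | 22 | 0.909 |
| 0.25 | 16 | 19 | 0.842 |
| 0.1 | 13.6 | 17.2 | 0.791 |

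Without the 2 added days (10 versus 14), the ratio is 19/21 = 0.905 at *d* = 0.5 and 14.5/17.5 = 0.829 at *d* = 0.25, so the added days matter little. Percentages of subjects with any event move less than counts. With 10 versus 14 days and an assumed 0.05 events per day, 1 − exp(−0.05 × 19) = 61.3% versus 1 − exp(−0.05 × 21) = 65.0% at *d* = 0.5.

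**Case B: the same planning means, with the gain coming from survival.** Assume that survivors in both arms are ventilated 7 days and spend 9 in ICU, that deaths occur in ICU at day 7, and that mortality is 50% in controls and 3/14 = 21.4% on poractant alfa. Survivors have 21 − 7 = 14 ventilator-free days and deaths score zero. The means are 0.5 × 14 = 7 and (11/14) × 14 = 11, exactly as planned.

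- Control: 0.5 × 7 + 0.5 × (9 + 19*d*)
- Poractant alfa: (3/14) × 7 + (11/14) × (9 + 19*d*)

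| *d* | Treated | Control | Ratio |
|---|---|---|---|
| 1 | 23.50 | 17.50 | 1.34 |
| 0.5 | 16.04 | 12.75 | 1.26 |
| 0.25 | 12.30 | 10.38 | 1.19 |
| 0.1 | 10.06 | 8.95 | 1.12 |

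The excess here comes from longer time alive; incomplete post-ICU capture partly offsets it. Crude counts mix the two effects.

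**The first 96 hours.** Doses at 0, 24 and 48 hours with readings 6, 12 and 24 hours after each give 6, 12, 24, 30, 36, 48, 54, 60 and 72 hours, which is the control list. From then on both arms move to 24-hourly readings. Treatment must start within 2 hours of randomisation (Protocol 7.1.2), so the two clocks nearly coincide. The window reaches 96 − 48 = 48 hours beyond the third scheduled dose.

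**The case against.** The strongest reply is that AE collection continues to the end of participation, with required checks after transfer. A ward chart is a retrospective record, so an unstated checking interval need not lose events. This stands as a limit on the point: at full capture Case A gives a ratio of exactly 1.00.

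A reader might go further than the documents allow in four ways:

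- **That the arm leaving ICU sooner must show fewer events, to the drug's advantage.** Case A needs incomplete capture, and Case B shows the same planning means pointing the other way.
- **That the planning figures imply 14 versus 10 ventilated days.** They do not. Patients who die or remain ventilated score zero (Protocol 8), so 21 minus the mean is not ventilated time.
- **That daily laboratory review stops at ICU discharge.** Safety laboratory tests are never daily.
- **That early deaths could hide harm.** Mortality (Table 14.2.4) and TEAEs leading to death (Table 14.3.2.10) are reported separately.

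It is also fair that fewer events after earlier discharge may be real benefit, and that the listings of TEAEs (16.2.7.2) and of hospital admission and discharge dates (16.2.6.5) allow a case-by-case look. Listings do not, however, give a like-for-like comparison between arms.

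**Conclusion.** The point holds as a limit on interpretation, not as a demonstrated bias. Surveillance is less intensive and of unstated frequency after ICU discharge, and SAP 10.2 compares crude counts across arms whose ICU stay and survival may differ.

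The possible distortion ranges from none to about 21% fewer recorded events in the shorter-stay arm under Case A. Under Case B the treated arm records about 12% to 26% more for capture from 10% to 50%, and 34% more at full capture. These ranges rest on assumed ICU stays, mortality, capture and equal event rates, and neither case is a forecast.

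The comparison presumes a populated control column, as the table shells intend, although the Safety Set as worded in SAP 6.1 covers only Curosurf-treated patients. That is a separate matter to reconcile.

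**What to change.** In SAP 10.2, add two tables restricted to TEAEs with onset within 96 hours of first dose (poractant alfa) or randomisation (control): the overview (as Table 14.3.2.1) and the SOC/PT table (as Table 14.3.2.2). Keep the full-period tables as the complete account. If the tables are added after the final SAP, explain them in the clinical study report, as SAP Section 1 provides for deviations.

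Do not add a rate per ICU patient-day. If its numerator is all TEAEs, a shorter stay inflates the rate. If it is ICU-onset events only, it conditions on a post-randomisation outcome that treatment may change.

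The cost is two tables from onset dates and times that SAP 10.2 already uses; no new data are needed. They do not show late events, and the documents do not say what share of patients is still alive and in ICU at 96 hours, so some difference in observation may remain inside the window.
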